7.2.3 Vital Signs and Physical Examination

Vital signs will be measured in semi-supine or supine position after at least 5 minutes of rest and will include respiratory rate, temperature, systolic and diastolic blood pressure, and pulse rate. Vital sign assessments can be repeated at the discretion of the PI or designee.

A complete physical examination will include, at a minimum, assessments of the skin, head and neck, cardiovascular, respiratory, gastrointestinal, and neurological systems. Please refer to the SoA ([Table 1](#)) as to when the assessments are required.

A brief physical examination will include, at a minimum, assessments of the skin, lungs, cardiovascular system, and abdomen (liver and spleen). Symptom-directed physical examinations will be completed at each follow-up visit at the discretion of the investigator.

Investigators will be instructed to pay special attention to clinical signs related to previous serious illnesses. Unscheduled physical examinations can be conducted at the discretion of the PI or designee.

7.2.4 12-Lead Electrocardiogram

The investigator or designee will perform ECG examinations at the timepoints listed in the SoA ([Table 1](#)).

Heart rate and PR, QRS, QT, and QTc intervals, etc., will be measured. Triplicate ECG will be taken if there are any clinically significant abnormalities detected by the physician in a single ECG.

Resting 12-lead ECGs should be recorded after the participant has been semi-supine or supine for a minimum of 5 minutes. ECGs will be interpreted on-site by the investigator to ensure participant safety. The PI (or designee) will evaluate ECG tracings to determine if they are normal, or if there are any clinically significant abnormalities. Site standard ranges will be used to determine if any parameters are considered out of range. ECGs can be repeated at the discretion of the PI or designee.

7.2.5 Pregnancy Testing

For female participant of childbearing potential, serum human chorionic gonadotropin (hCG) will be tested at the Screening, Baseline (Day 1), Week 2 (Day 15), Week 4 (Day 29) visits, and at selected follow-up visits. In addition, urine hCG test must be performed prior to each dosing visit. Following a negative pregnancy test result at Screening, appropriate contraception must be initiated or continued (for participant already on contraceptives) and maintained until 6 months after the last dose of study treatment.

Serum pregnancy tests will also be performed additionally whenever potential pregnancy is suspected. Additional pregnancy tests may also be undertaken if requested by the IEC or if required by local regulations. In the case of a positive confirmed pregnancy, the pregnancy will be immediately reported to the Sponsor and the participant will be followed up until completion or termination of the pregnancy (see [Section 8.4](#)).

7.3 Efficacy Assessments

To ensure consistency and reduce variability, the same evaluator should perform all investigator's assessments for a given participant throughout the study where feasible. Should it be necessary, another physician designated and trained by the investigator may conduct the above assessments in the investigator's absence.

7.3.1 Eczema Area and Severity Index (EASI)

The EASI is a validated composite scoring system assessed by the investigator based on the body area involved in each of the four body regions (head and neck, upper limbs, lower limbs, and trunk) and the average severity of each of the four key signs of AD (erythema, edema/papulation, excoriation, and lichenification) based on a 4-point scale of 0 (none), 1 (mild), 2 (moderate), and 3 (severe), (Hanifin 2001). Symptoms (e.g., pruritus) and secondary signs (e.g., xerosis, scaling) are excluded from the assessment. The total EASI score ranges from 0 (clear or no eczema) to 72 (maximum severity), with the higher values indicating more severe and/or extensive disease. A score of 0 to 72 will be recorded. All assessments will be recorded in the eCRF according to the completion guidelines.

The EASI will be assessed by the investigator at selected scheduled and unscheduled clinic visits. Further details on EASI will be provided in the Investigate Site File Binder.

7.3.2 Investigator Global Assessment (IGA)

The IGA is intended to assess the global severities of key acute clinical signs of AD, including erythema, induration/papulation, oozing/crusting (lichenification excluded) based on a 5-point scale of clear (0), almost clear (1), mild (2), moderate (3) and severe (4). A grade of 0 to 4 will be scored by the investigator. Assessments will be recorded in the eCRF.

The IGA will be performed by the investigator at selected scheduled clinic visits. Further details on IGA will be provided in the Investigate Site File Binder.

7.3.3 SCORing Atopic Dermatitis (SCORAD)

The validated SCORAD index uses the rule of nines to assess disease extent and evaluates six clinical characteristics to determine disease severity: (1) erythema, (2) edema/papulation, (3) oozing/crust, (4) excoriation, (5) lichenification, and (6) dryness (ETFAD 1993). The SCORAD index also assesses subjective symptoms of pruritus and sleep loss. These three domains (extent of disease, disease severity, and subjective symptoms) combine to give a maximum possible score of 103. Assessments will be recorded in the eCRF.

The SCORAD will be assessed at selected scheduled clinic visits. Further details on SCORAD will be provided in the Investigate Site File Binder.

7.3.4 Body Surface Area (BSA)

The BSA assessment estimates the extent of disease or skin involvement with respect to AD and is expressed as a percentage of total body surface. BSA will be determined by the investigator using the rule of nines.

Participant will undergo this assessment at selected scheduled clinic visits. Further details on BSA will be provided as a component of SCORAD assessments in the Investigate Site File Binder.

7.3.5 Itch and Sleep Quality Numerical Rating Scale

At scheduled and unscheduled clinic visits, participants will assess the worst intensity itch due to AD per an NRS (WI-NRS, where 0 = “none” and 10 = “worst imaginable”) [REDACTED]
[REDACTED].

At scheduled clinic visits, participants will assess sleep quality per an NRS (SQ-NRS, where 0 = “best possible sleep” and 10 = “worst possible sleep”) [REDACTED]
[REDACTED].

Further details on WI-NRS and SQ-NRS will be provided in the Investigate Site File Binder.

7.3.6 Patient Global Impression of Severity (PGIS) of AD

At the scheduled clinical visits, participants will rate the severity of their AD over the past week on a 5-point scale ranging from 0 = “none” to 4 = “very severe”.

Further details of assessments will be provided in the Investigate Site Files Binder.

7.3.7 Patient Global Impression of Change (PGIC) of AD

At the scheduled clinical visits, participants will rate the change in their AD on a 5-point scale ranging from 1 = “much better” to 5 = “much worse”. Participants will be asked to provide this rating in comparison to just before the participant started taking study treatment.

Further details of assessments will be provided in the Investigate Site File Binder.

7.3.8 Dermatology Life Quality Index (DLQI)

The DLQI is a validated 10-question instrument used to measure the impact of skin disease on the quality of life (QoL) of an affected person over the previous week. The ten questions cover the following topics: symptoms, embarrassment, shopping and home care, clothes, social and leisure, sport, work or study, close relationships, sex, and treatment ([Finlay, Khan. 1992](#)). The DLQI score ranges from 0 (no impact of skin disease on QoL) to 30 (maximum impact on QoL).

The DLQI is completed by the participant in the study clinic. Assessments will be recorded in the eCRF. Further details of DLQI will be provided in the Investigate Site Files Binder.

7.3.9 Atopic Dermatitis Lesion Photography

AD lesion photographs of a representative area of AD involvement which reflects the overall severity of disease (e.g., based on investigator’s global assessment or SCORAD assessment) will be taken at Baseline (Day 1, pre-dose). Subsequent photographs of the same area will be taken at Week 12 (Day 85)/EOT and Week 24 (Day 169)/EOS. Additional photographs, especially those recording specific changes noted are also encouraged, if the participant is willing. AD lesion photography assessment is optional, but is encouraged, for participants in this study.

The photographs may be included in the clinical study report, regulatory submission documents, scientific publications, or in other public communications of clinical data to show changes in clinical presentations following treatment with IMG-007.

Instructions for taking the photographs are provided in the Photography Manual.

7.4 Pharmacokinetics and Immunogenicity Assessments

Blood will be collected to describe the IMG-007 PK and immunogenicity profiles as outlined in [Table 5](#).

Participants with signs of any potential immune response to IMG-007 will be closely monitored with clinical evaluations. The PK and ADA samples may be collected at unscheduled visits for further evaluation.

Details concerning handling of PK and ADA serum samples, including labeling and shipping instructions, will be provided in the Laboratory Manual. The actual time each sample was collected will be captured to the nearest minute in the eCRF and recorded in the database.

Samples will be shipped to the laboratory where samples will be analyzed for serum IMG-007 concentrations using a validated method.

Validated screening and confirmatory assays will be employed to detect ADAs at multiple timepoints throughout the study.

The immunogenicity evaluation will utilize a risk-based immunogenicity strategy ([Bai et al. 2012](#); [Rosenberg et al. 2004](#)) to characterize ADA responses to IMG-007 in support of the clinical development program.

Table 5 PK and ADA Sampling Schema

Dose No.	Day	Pre-dose /Post-dose	PK blood sampling time	ADA sampling time	Sampling Window
1	1	Pre-dose	0 (pre-dose)	0 (pre-dose)	- 2 hours
	1	Post-dose	EOI	--	+10 mins
	8	Post-dose	7 days post-dose	--	± 3 days
2	15	Pre-dose	0 (pre-dose)	0 (pre-dose)	- 2 hours
	15	Post-dose	EOI	--	+10 mins
3	29	Pre-dose	0 (pre-dose)	0 (pre-dose)	- 2 hours
	29	Post-dose	EOI	--	+10 mins
	43	Post-dose	14 days post-dose	14 days post-dose	± 3 days
57	Post-dose	28 days post-dose	28 days post-dose	± 3 days	
	85/EOT	56 days post-dose	56 days post-dose	± 3 days	
113	Post-dose	84 days post-dose	84 days post-dose	± 3 days	
141	Post-dose	112 days post-dose	112 days post-dose	± 3 days	
169/EOS	Post-dose	140 days post-dose	140 days post-dose	± 3 days	

Abbreviations: ADA = anti-drug antibody; EOI = end of Infusion; EOT = end of treatment; EOS = end of study; PK = pharmacokinetic

7.5 Pharmacodynamics Assessments

7.5.1 Circulating Biomarkers

Blood samples will be sampled for biomarker analysis.

Blood samples for analysis of receptor occupancy (RO) will be collected at Baseline (Day 1, pre-dose and end of infusion [EOI]), Week 1 (Day 8), Week 2 (Day 15, pre-dose and EOI), Week 4 (Day 29, pre-dose and EOI), Week 6 (Day 43), Week 8 (Day 57), Week 12 (Day 85)/EOT, Week 16 (Day 113), Week 20 (Day 141), and Week 24 (Day 169)/EOS.

Blood samples for analysis of inflammatory markers including TARC will be collected at Baseline (Day 1, pre-dose), Week 1 (Day 8), Week 2 (Day 15, pre-dose), Week 4 (Day 29, pre-dose), Week 6 (Day 43), Week 8 (Day 57), Week 12 (Day 85)/EOT, Week 16 (Day 113), Week 20 (Day 141), and Week 24 (Day 169)/EOS.

The sampling window for PD assessments of RO and inflammatory markers are as defined in [Table 5](#). Details concerning the handling of blood samples, including labeling and shipping instructions are provided in the Laboratory Manual.

7.5.2 Atopic Dermatitis Lesion Biopsy

AD lesion biopsy is optional, but is encouraged, for participants in this study. At Screening, participants who are willing to provide skin biopsies will indicate their consent for biopsy in the ICF. Skin biopsy samples from lesional skin will be collected at the Baseline (Day 1, pre-dose), Week 12 (Day 85)/EOT, and Week 24 (Day 169)/EOS visits. The biopsy should be sampled under instructions outlined in the Laboratory Manual.

Skin biopsies will be analyzed for transcriptome sequencing, immunohistochemical staining for skin thickness, keratin (K)16, OX40, and OX40L.

8 COLLECTION OF ADVERSE EVENTS AND SAFETY REPORTING

The PI should make sure that all the staff involved in the study are familiar with the content of this section.

The investigator and any qualified designees are responsible for detecting, documenting, and recording events that meet the definition of an AE or SAE and remain responsible for following up.

The term AE is used to include both serious and non-serious AEs if not specified.

8.1 Definitions

8.1.1 Adverse Event

An AE is the development of any untoward medical occurrence in a patient or clinical study participant who is administered with a medicinal product that does not necessarily have a causal relationship with this treatment. An AE can therefore be any unfavorable and unintended sign, symptom, or disease temporally associated with the use of a medicinal product, whether or not considered related to the medicinal product, including the following conditions:

- 1) Any newly occurred undesirable medical condition (including newly diagnosed disease or signs and symptoms when a diagnosis is pending);
- 2) Exacerbation of a chronic or intermittent pre-existing condition including either an increase in frequency and/or intensity of the condition. However, events that are unequivocally due to natural disease progression of the underlying disease being studied should not be reported as an AE during the study unless judged by the investigator to be more severe than expected for the participant condition;
- 3) Clinically significant laboratory abnormality (see [Section 8.2.3](#)).

8.1.2 Serious Adverse Event

An SAE is defined as any untoward medical occurrence that, at any dose, meets one or more of the criteria listed:

- **Results in death**

Death is the outcome and therefore always record the medical condition that results in the fatal outcome as the SAE term.

Deaths with an unknown cause should be reported as SAE “death with unknown cause”. Every attempt should be tried to obtain the cause of death. A postmortem may be helpful in the assessment of the cause of death, and if performed, a copy of the autopsy report should be forwarded to the Sponsor.

- **Is immediately life threatening**

The term “life threatening” in the definition of seriousness refers to an event in which the participant was at risk of death at the time of the event. It does not refer to an event, which hypothetically might have caused death, if it were more severe.

- **Requires in-patient hospitalization or prolongation of existing hospitalization**

In general, hospitalization signifies that the participant has been admitted (usually involving at least an overnight stay) at the hospital or emergency ward for observation and/or treatment that would not have been appropriate in the physician’s office or outpatient setting. Complications that occur during hospitalization are AEs. If a complication prolongs hospitalization or fulfills any other serious criteria, the event is serious. When in doubt as to whether hospitalization occurred or was necessary, the AE should be considered serious.

The following situations are NOT considered as hospitalizations or prolongation of existing hospitalization that meet SAE criteria:

- Hospitalization for elective treatment of a pre-existing condition that did not worsen from baseline;

- Protocol specified admission. Routine clinical management for mild to moderate laboratory tests abnormality at scheduled visits will not be regarded as leading to prolonged hospital stay and should be reported as non-serious AE according to the definition of AE;
- Hospitalizations are within the local medical practice for medical insurance purpose while the disease treated would normally be an outpatient practice (e.g., hospitalization for a common cold as local medical insurance can cover).

All pre-planned hospitalizations need to be documented in the participant records at Baseline. All hospitalization during the study should be documented with a clear statement indicating that this hospitalization fulfills the SAE exemption specified in the protocol.

- **Results in persistent or significant disability or incapacity**

The term disability means a substantial disruption of a person's ability to conduct normal life functions.

- **Is a congenital abnormality or birth defect**

This is applicable to any congenital anomaly/birth defect in a neonate born to a female participant exposed to study treatment, or the female partner of a male participant exposed to study treatment. See more information in [Section 8.4](#).

- **Is an important medical event** that may jeopardize the participant or may require medical treatment to prevent one of the outcomes listed above.

Medical and scientific judgment should be exercised in deciding whether a case is serious in situations where important medical events may not be immediately life threatening or result in death, hospitalization, disability, or incapacity but may jeopardize the participant or may require medical treatment to prevent one or more outcomes listed in the definition of seriousness. These should usually be considered as serious.

All SAEs will be reported to the Sponsor or designee within 24 hours by the investigator after being aware of. The investigator will submit any updated SAE data to the Sponsor within 24 hours of it being available. Please see more information in [Section 8.3](#).

8.1.3 Adverse Event Variables

The following variables will be collected for each AE:

- AE (verbatim)
- The date when the AE started and stopped
- The maximum severity reported or changes in severity (report only the maximum severity for a calendar day). See [Section 8.1.4](#) for severity assessment.
- Whether the AE is serious or not

- Investigator causality rating against the study treatment (yes or no). See [Section 8.1.5](#) for causality assessment.
- Action taken with regard to study treatment
- Administration of treatment for the AE
- Outcome

In addition, the following variables will be collected for SAEs, either on the eCRF or SAE reporting form:

- Date the AE meeting the criteria for SAE (SAE onset date)
- Date the investigator becoming aware of the SAE
- Seriousness criteria
- Date of hospitalization
- Date of discharge
- Probable cause of death
- Date of death
- Whether an autopsy was performed
- Causality assessment in relation to study procedure(s)
- Causality assessment in relation to other medication
- Description of the SAE

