8.2.1 Time Period and Frequency for Collecting Adverse Events

The follow-up period is defined as up to Day 169/EOS. All AEs/SAEs will be collected from the time the participant signs the ICF. After the follow-up period, any SAE that is related to study treatment by investigator assessment should be reported directly to the Sponsor's pharmacovigilance team.

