11.3.1 Analysis of Safety

Safety variables including incidence and severity, and duration of TEAEs and changes from baseline of relevant parameters (such as vital signs, ECGs, and clinical laboratory values) will be summarized.

- AEs will be coded using the Medical Dictionary for Regulatory Activities (MedDRA, version currently in use by the Sponsor at the time of database lock). TEAEs are defined as events started after initiation of the first dose of study treatment or events present that worsen after the start of dosing. The number and proportion of participants experiencing one or more TEAEs will be summarized by severity, and relationship to study treatment.
- Prior and concomitant medications (including rescue medications) will be coded using the World Health Organization Drug Dictionary (WHODrug). The number and proportion of participants taking prior and/or concomitant medications will be summarized.
- Vital sign (systolic and diastolic blood pressure, pulse, respiratory rate, and temperature) and ECG parameters will be summarized by visit descriptively. Changes from baseline, number, and proportion of participants with clinically important values will be presented descriptively.
- Clinical laboratory parameters will be summarized using descriptive statistics, by changes from baseline, post-dosing shift from Baseline (Day 1) in the normal or abnormal category of laboratory values by visit, and number and proportion of participants with a treatment-emergent clinically significant abnormal value based on predefined criteria, and data listings.

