4.6 Safety Variables

4.6.1 Adverse Events and Serious Adverse Events Variables

Adverse events and serious adverse events will be collected from the time of informed consent signature until the end of the study. All adverse events will be coded according to the latest available version (26.0 or higher) of MedDRA.

An **Adverse Event** is the development of any untoward medical occurrence in a participant or clinical study participant who is administered with a medicinal product that does not necessarily have a causal relationship with this treatment. An AE can therefore be any unfavorable and unintended sign, symptom, or disease temporally associated with the use of a medicinal product, whether or not considered related to the medicinal product, including the following conditions:

- 1) Any newly occurred undesirable medical condition (including newly diagnosed disease or signs and symptoms when a diagnosis is pending);
- 2) Exacerbation of a chronic or intermittent pre-existing condition including either an increase in frequency and/or intensity of the condition. However, events that are unequivocally due to natural disease progression of the underlying disease being studied should not be reported as an AE during the study unless judged by the investigator to be more severe than expected for the participant condition;
- 3) Clinically significant laboratory abnormality.

A **Serious Adverse Event** is defined as any untoward medical occurrence that, at any dose, meets one or more of the criteria listed:

- **Results in death**
- **Is immediately life threatening**
- **Requires in-patient hospitalization or prolongation of existing hospitalization**
- **Results in persistent or significant disability or incapacity**
- **Is a congenital abnormality or birth defect**
- **Is an important medical event** (i.e., that may jeopardize the participant or may require medical treatment to prevent one of the outcomes listed above.)

Details for each criterion above are presented in the study protocol section 8.1.2.

Non-treatment emergent AEs (non-TEAEs) are AEs that are developed or worsened in severity compared to the baseline during the period between participant enrolment and study drug administration. all AEs collected during the screening period are considered as non-TEAEs.

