Treatment-emergent AEs (TEAEs) are AEs that developed or worsened in severity compared to the baseline during the treatment and follow-up period. As only the worsening pre-existing AEs and new AEs reported during the treatment and follow-up period will be collected in the study, all AEs collected during the treatment and follow-up period are considered as TEAEs.

TEAE that are infusion related reaction will be summarized. These TEAEs are localized injection/infusion reactions that may include pruritus, pain, erythema, swelling, rashes, or bleeding around the injection/infusion site. Systemic injection/infusion-related reactions may be immediate type or delayed type immune complex-associated hypersensitivity reactions (e.g., serum sickness).

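### SAP 4.6.1 classes every screening AE as non-treatment-emergent, and Protocol 8.1.3 does not ensure that worsening after the first infusion appears as a separate record

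*Protocol*

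**What the plan says.** The primary endpoint is the incidence of TEAEs (Protocol Section 3).

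**Definition.** Protocol 11.3.1, and the synopsis in the same terms, counts as treatment-emergent both new events and "events present that worsen after the start of dosing". SAP 4.6.1 agrees: TEAEs are "AEs that developed or worsened in severity compared to the baseline during the treatment and follow-up period".

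**Collection.** Protocol 8.2.1 states: "All AEs/SAEs will be collected from the time the participant signs the ICF". Screening AEs are therefore on the AE form, and screening can last up to 35 days. Protocol 8.1.3 lists the variables for each AE. They include "The date when the AE started and stopped" and, for severity, "The maximum severity reported or changes in severity (report only the maximum severity for a calendar day"). No date of worsening is listed, although for SAEs the same section does collect the date on which the event became serious.

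**Classification.** SAP 4.6.1 converts the definition into a rule by period. For screening, "all AEs collected during the screening period are considered as non-TEAEs". For treatment and follow-up, every collected AE is a TEAE, on this reasoning: "As only the worsening pre-existing AEs and new AEs reported during the treatment and follow-up period will be collected in the study".

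**The concern.** The definition depends on whether the event got worse after dosing began. The SAP rule depends on the period in which the event was collected. The two agree only if every post-dose worsening of a screening AE enters the database as its own treatment-period record. The SAP assumes this, but no instruction in either document requires it.

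Where the assumption fails, the error for these events runs one way. Worsening on drug drops out of the TEAE, grade 3 or higher, and treatment-related tables (SAP 6.9.1) and out of the TEAE tables for the Safety Review Committee (SAP 9.2). It appears among the non-TEAEs instead. A single record also carries a single causality rating, and an onset before any exposure counts against relatedness under the time-course factor in Protocol 8.1.5.

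**Working it through.** Neither document states a figure that depends on this point, so there is nothing to reproduce. The check is a comparison of rules, followed by an illustration of size.

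**Step 1. Recording options.** Take an AE that starts in screening, is ongoing at the first infusion and then rises in grade. Protocol 8.1.3 leaves three ways to record it:

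| Site practice | By the TEAE definition | By the SAP period rule |
|---|---|---|
| New record at worsening | TEAE | TEAE |
| One record, severity changes noted | TEAE, derivable if the changes are dated | non-TEAE |
| One record, maximum severity only | TEAE, but not derivable: grade at first dose and date of worsening are unknown | non-TEAE |

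The last column reads the period rule by when the event was first reported. In the second and third rows the definition and the rule disagree.

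**Step 2. Does another convention rescue the record?** SAP 12.2 can move a partial or missing start date to the first dose. A complete screening start date is left as it is, so that route does not help here.

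**Step 3. Size for one participant.** Protocol 4.1 gives 13 enrolled, all in Cohort 1. One participant wrongly left out is 1/13 = 7.7 percentage points, and two are 2/13 = 15.4. As an illustration, incidence falls from 10/13 = 76.9% (95% Clopper-Pearson interval 46.2 to 95.0) to 9/13 = 69.2% (38.6 to 90.9). Counting is by participant, so this happens only if the participant has no other TEAE.

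**Step 4. How likely is a shift in the primary incidence?** Let q be the chance that a participant has a screening AE that worsens after dosing and is kept as one record, and p the chance of some other TEAE. Assuming the two are independent, the chance that at least one of 13 is lost is 1 − (1 − q(1 − p))^13. Neither q nor p is in the documents for this population. For p, I borrow 22/30 = 73.3% from the healthy-participant study (Protocol 2.2) as an assumption:

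| q (assumed) | q(1 − p) | Chance that at least one of 13 is lost |
|---|---|---|
| 2% | 0.53% | 6.7% |
| 5% | 1.33% | 16.0% |
| 10% | 2.67% | 29.6% |
| 20% | 5.33% | 51.0% |

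With p from 50% to 90% and the same q values, the chance runs from 2.6% to 74.6%. The range is wide because the inputs are guesses.

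**Step 5. Tables below the headline rate.** These can change even when the participant has another TEAE. SAP 6.9.1 tabulates preferred terms seen in at least 2 participants, so losing one record can take a term from 2 to 1 and off that table.

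**The case against.** A reader might infer that Protocol 8.1.3 rules out a new record, so that these events will be misfiled. The documents do not support that. Section 8.1.3 is silent on when a new record is opened, and it offers severity changes as an alternative to the maximum. Its calendar-day clause makes most sense if changes are tracked by date.

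Other text points towards worsening being reported. Protocol 8.1.1 includes as an AE "Exacerbation of a chronic or intermittent pre-existing condition including either an increase in frequency and/or intensity of the condition", and Protocol 8.2.3.2 requires aggravated examination findings, compared with Baseline, to be reported. The SAP sentence just before the screening rule confines non-TEAEs to events that arise or worsen before study drug. The intended classification is therefore the right one. The eCRF completion guidelines and the data management plan, where record-opening rules usually sit, are not available here.

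Nor do the documents show that any such event occurred. Washout flares are a weak example, because Protocol 8.1.1 excludes natural progression of the disease under study unless it is more severe than expected. Non-TEAEs are also tabulated and listed, so a misclassified event stays visible among 13 participants.

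Most of this stands, and it limits the point to a conditional risk. It does not remove it. Saying that an exacerbation is an AE does not settle whether an AE already on the form gets a second record or an updated grade. The screening rule has no exception, so a programmer applying it literally would override the definition.

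**Conclusion.** The point holds as an inconsistency between definition and rule that takes effect under a recording practice the protocol permits. It arises from Protocol 8.1.3 and the SAP 4.6.1 period rule together. Section 8.1.3 alone would not cause it, and a certain loss of events should not be read into it. If sites opened new records on worsening, nothing changes.

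If they did not, each affected participant with no other TEAE moves the primary incidence by 7.7 points, and the finer safety tables may change in any case. The number affected is unknown and may be zero. The trial is single-arm, with a sample size set by feasibility and no stated power, so no power or error-rate figure is touched. It should be corrected before lock because it bears on the primary endpoint and is cheap to settle.

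**What to change.** 1. **SAP 4.6.1, before database lock.** Replace the screening sentence with: *An AE first reported in screening is a non-TEAE unless its severity after the first dose exceeds its severity at first dose; in that case it is a TEAE from the date of worsening.*
2. **Data queries.** For each AE with onset before the first dose that was ongoing at that dose, ask for its grade at that time and any date of worsening.
3. **If the eCRF guidelines already require a new record on worsening,** cite that rule in SAP 4.6.1. That closes the point.
4. **Protocol 8.1.3.** A forward-looking requirement for a new record or a dated severity change is secondary. Enrolment ended on 31 January 2024 and the current protocol is dated 14 June 2024, so little of the treatment and follow-up time remains for it to act on. It is worth carrying into the next study.

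The cost is one SAP sentence and a small number of queries in 13 participants. TEAE incidence may be slightly higher, which would be the correct reading of the protocol's own definition.
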